5.4 SCREEN FAILURES

Screen failures will only be allowed in exceptional circumstances. Potential participants who screen-failed based on the Inclusion Criteria will not be allowed to re-screen. Only potential participants who screen-failed based on the Exclusion Criteria 4, 5 or 6 will be allowed to re-screen if they no longer meet the Exclusion Criteria.

5.5 STRATEGIES FOR RECRUITMENT AND RETENTION

Achieving target enrollment. It is not anticipated that there will be difficulty screening enough participants to meet the enrollment target of a total of 40 participants in this study. The goal will be to enroll approximately equal numbers of males and females, and to enroll a participant population representative of the sex, racial and ethnic mix of patients with NAFLD at the two clinical sites participating in this study. No special stratification will be done based on sex or race. Our effective screen-fail rate is expected to be up to about 25%, taking into account failure to satisfy inclusion and exclusion criteria, loss of participants due to possible uneven filling of our three enrollment categories, dropout, and technical failure. Thus, we expect to need to screen 50 participants to achieve our target enrollment of 40 participants.

Anticipated accrual rate. We anticipate being able to enroll one participant at each site every 2 weeks, and therefore expect to be able to complete enrollment in about 40 weeks.

Number of sites. There will be two clinical sites in this study (MGH and UCSD), and both have agreed to participate.

Source of participants. Participants at MGH will be recruited from EMR review and the Fatty Liver Disease Clinic. Participants at UCSD will be recruited from the UCSD NAFLD Research Center.

Methods of identification and approach for potential participants. At both sites, recruitment may be by informational flyers placed at the recruitment venues and/or by physicians at those venues discussing possible participation in this study with potential participants. Patients identified through EMR review may be approached via opt-out mailing sent on behalf of their primary physician. If subjects do not opt-out they will be contacted by study staff.

Recruitment strategies. It is not anticipated that additional recruitment methods or strategies will be needed to achieve our planned target enrollment within one year.

Participant retention. Given the short participation period for each participant (i.e., about a week or less to complete both imaging visits), it is not anticipated that participant retention will be a problem in this study.

Recruitment and retention of participants from historically under-represented populations. Given the expected strong ability to recruit fairly from the outpatient clinic populations at both sites, the disproportionate prevalence of NAFLD in Latino minorities, and the short duration of participant involvement in this study, we do not expect that recruitment or retention of participants from historically under-represented populations will be a problem for this study.

Vulnerable populations. No subjects from vulnerable populations will be recruited for this study.

Participant compensation. Participants will be given up to \$50 per hour for their participation in this study to compensate them for their time, any inconvenience, and parking. Compensation will be made upon completion of all study procedures or after completion of screening if participant screen fails.

6 STUDY INTERVENTION

6.1 STUDY INTERVENTION(S) ADMINISTRATION

6.1.1 STUDY INTERVENTION DESCRIPTION

Study interventions will include questionnaires, anthropometric measurements, blood collection, and non-invasive ultrasound-based imaging exams. All ultrasound-based devices use energies below FDA limits for diagnostic ultrasound.

6.1.2 DOSING AND ADMINISTRATION

There will be no dosing or administration of investigational products as part of this study.

6.2 PREPARATION/HANDLING/STORAGE/ACCOUNTABILITY

6.2.1 ACQUISITION AND ACCOUNTABILITY

There is no study intervention other than ultrasound-based exams. All ultrasound-based exams will be acquired by trained operators.

6.2.2 FORMULATION, APPEARANCE, PACKAGING, AND LABELING

This section is not applicable as there is no study interventional product.

6.2.3 PRODUCT STORAGE AND STABILITY

This section is not applicable as there is no study interventional product.

6.2.4 PREPARATION

This section is not applicable as there is no study interventional product.

6.3 MEASURES TO MINIMIZE BIAS: RANDOMIZATION AND BLINDING

Study participants will not be randomized to individual treatment groups or be blinded. In order to ensure a uniform distribution of scanner combinations, participants will follow a block-randomization pattern with different scanner combinations for different participants, however, patients and operators will not be blinded to ultrasound scanners being used.

All efforts will be made to keep ultrasound operators blinded to clinical and laboratory data, however, it is not believed that this will significantly affect the ultrasound acquisition. The Visit 2 operator will be asked to not review the Visit 1 exam results.

Central analysts will be blinded to key clinical and laboratory findings to minimize potential bias. Blinding of the central analysts will be outlined in a separate Image Review Charter.

6.4 STUDY INTERVENTION COMPLIANCE

Acquisition and analysis of ultrasound exams will be captured in a separate Acquisition Manual and Image Review Charter. These documents will outline the acquisition procedures and ultrasound analysis procedures.

Participant weight will be measured and interim medical history, medication use, alcohol use, physical activity will be ascertained at each visit to assess compliance by participants with instructions to maintain steady-state weight, exercise, alcohol use, and medications.

6.5 CONCOMITANT THERAPY

Current medications will be collected as part of a participant's medical history.

6.5.1 RESCUE MEDICINE

As there is no study intervention, no rescue medication will be used.

7 STUDY INTERVENTION

7.1 DISCONTINUATION OF STUDY INTERVENTION

If participants become intolerant to ultrasound scanning they may discontinue. If they have not completed Visit 2 they will be withdrawn from the study.

7.2 PARTICIPANT DISCONTINUATION/WITHDRAWAL FROM THE STUDY

Participants are free to withdraw from participation in the study at any time upon request.

An investigator may discontinue or withdraw a participant from the study if, in the opinion of the investigator, there have been significant lifestyle changes or other factors that could affect study results.

7.3 LOST TO FOLLOW-UP

A participant will be considered lost to follow-up if he or she fails to return for Visit 1 and/or Visit 2, and is unable to be contacted by the study site staff.

The following actions must be taken if a participant fails to return to the clinic for a required study visit:

- The site will attempt to contact the participant and reschedule the missed visit within the specified time frame and counsel the participant on the importance of maintaining the assigned visit schedule and ascertain if the participant wishes to and/or should continue in the study.
- Should the participant continue to be unreachable, he or she will be considered to have withdrawn from the study with a primary reason of lost to follow-up.

If a participant is lost to follow-up and has only completed one study visit, they may or may not be replaced as part of the targeted enrollment. This decision will be based on the number of subjects who have completed the study to date.

8 STUDY ASSESSMENTS AND PROCEDURES

8.1 SCREENING AND EFFICACY ASSESSMENTS

Several assessments will be completed across Screening, Visit 1 and Visit 2. These are listed below and specific ultrasound image acquisition will be outlined in the 'NIMBLE 1.1 Ultrasound Imaging Manual'.

- **Demographics, anthropometrics and medical history will be collected at the Screening Visit**
- **Physical examination**
 - Height will be recorded at Screening.
 - Weight and vital signs will be recorded at each visit.
 - Body mass index will be calculated at each visit.
 - All measurements will be made by trained coordinators using standard and calibrated instruments.
- **Imaging assessments will be collected at Visit 1 and Visit 2**

Ultrasound based imaging parameters will be collected from all patients in two visits. These will include but may not be limited to:

- **Shear wave elastography results in m/s and/or kPa**
- **Quantitative ultrasound parameters, where available, including:**

- Attenuation Coefficient
- Backscatter Coefficient
- Shear Wave Dispersion
- Speed of Sound
- Ultrasound derived fat fraction
- **Conventional B mode (gray-scale) and Doppler ultrasound images, including:**
 - An image of the liver and right kidney on the same image for hepato-renal index calculation
 - Right liver lobe for skin to liver capsule distance calculation
 - Portal vein Doppler for portal vein pulsatility index measurement
- **VCTE and Controlled Attenuation Parameter measurements with the Fibroscan system**

Measurements will be collected using the following systems:

- Ultrasound devices:
 - GE LOGIQ E10
 - Siemens Sequoia
 - Canon Aplio i800
 - Philips EPIQ 7
 - SuperSonic Aixplorer Mach 30
- VCTE
 - Fibroscan 530 Compact

For detailed ultrasound image acquisition protocol, please refer to the 'NIMBLE 1.1 Ultrasound Imaging Manual'. Note: Ultrasound-based exams will be reviewed centrally and results will not be shared with study participants.

- **Biological specimen collection and laboratory evaluations will be collected at the Screening Visit.**
 - Blood will be collected by trained phlebotomists at each site using routine methods and standard collection tubes.
 - Total volume is expected to be about 10 mL or less
 - Blood collected at MGH will be analyzed by the MGH clinical laboratory.
 - Blood collected at UCSD will be analyzed by the UCSD clinical laboratory.
 - Blood results obtained within the 3-month interval prior to the screening visit at the MGH or UCSD laboratories will be considered acceptable for study analyses and may be used at PI discretion.
 - For each laboratory, the normal ranges for each blood test will be recorded and filed
- **Special assays or procedures required**
 - None
- **Administration of questionnaires or other instruments**
 - The following questionnaires will be administered at Screening:
 - Medical history questionnaire
 - Medication use questionnaire
 - Alcohol consumption questionnaire (AUDIT questionnaire)
 - Physical activity questionnaire
 - The following questionnaires will be administered at Visit 1 and Visit 2:

- Interim medical history questionnaire
- Change in medication use questionnaire
- Change in physical activity questionnaire

8.2 SAFETY AND OTHER ASSESSMENTS

Laboratory values will be reviewed by the PI at each site. The PI will report clinically important incidental findings to the referring physician or, if there is no referring physician, to the participant.

If a lesion is identified by the operator during real-time scanning the site PI will be alerted by study staff and will review the images for safety.

Additionally, ultrasound images will be reviewed by a central reviewer. The purpose of this review is to evaluate images for liver stiffness and other exploratory biomarkers relevant to NAFLD and NASH. Central image review is not a complete medical review of the subject. If during the central review process, an unexpected observation is identified and this finding could, in the opinion of the central reviewer, have a significant health or reproductive consequence, this finding may be shared with the principal investigator.

All follow-up testing and final diagnosis will be left to the discretion of the medical professionals at the site or those with an existing physician-patient relationship. The principal investigator will be responsible for reporting any adverse events identified from incidental findings as described in the Adverse Event Reporting section. Identification of such incidental findings during the central review process should not be expected, and the site maintains responsibility for performing a general safety review of all images as per site protocols.

There are no dedicated Safety Assessments as part of this study as this study does not involve study medication.

8.3 ADVERSE EVENTS AND SERIOUS ADVERSE EVENTS

8.3.1 DEFINITION OF ADVERSE EVENTS (AE)

An AE is any untoward or unfavorable medical occurrence in a human subject, including any abnormal physical exam or certain unexpected abnormal laboratory finding, symptom, or disease, temporally associated with a subject's participation in the research.

In this clinical study, we anticipate only minimal risk of adverse events because the investigational procedure is limited to noninvasive diagnostic ultrasound imaging of the abdomen using the vendor specific investigational liver fat quantification and shear wave elastography/VCTE software. All ultrasound systems that will be used in this clinical trial use ultrasound energies below FDA limits for diagnostic ultrasound. At these energies, these ultrasound systems and software have no known bioeffects and are not expected to cause risk to participants.

Anticipated nonserious AEs may include;

- Potential discomfort during the ultrasound scans due to body positioning, and

- Potential discomfort during the ultrasound scans due to ultrasound transducer pressure.
- Potential discomfort related to IV stick following blood draw at screening

8.3.2 DEFINITION OF SERIOUS ADVERSE EVENTS (SAE)

A SAE is any AE that:

1. Results in death, or
2. Is life-threatening, or
3. Results in hospitalization or prolongation of existing hospitalization, or
4. Results in a persistent or significant disability/incapacitation, or
5. Results in a congenital anomaly/birth defect, or
6. May jeopardize the participant's health and may require medical or surgical intervention to prevent one of the other outcomes listed above.

No SAEs are anticipated in this clinical trial.

8.3.3 CLASSIFICATION OF AN ADVERSE EVENT

8.3.3.1 SEVERITY OF EVENT

For adverse events (AEs), the following guidelines are used to describe severity.

Mild - Events require minimal or no treatment and do not interfere with the participant's daily activities.

Moderate - Events result in a low level of inconvenience or concern with the therapeutic measures. Moderate events may cause some interference with functioning.

Severe - Events interrupt a participant's usual daily activity and may require systemic drug therapy or other treatment. Severe events are usually potentially life-threatening or incapacitating. Of note, the term 'severe' does not necessarily equate to 'serious'.

AEs will be assessed by site PIs using the criteria mentioned above. Site PIs are responsible for reporting and managing AEs.

8.3.3.2 RELATIONSHIP TO STUDY INTERVENTION

All AEs will have their relationship to study procedures assessed by the site principal investigator. The following criteria will be used to identify causality; (0) Not related, (1) Unlikely to be related, (2) Potentially related, (3) Potentially related, (4) Probably related, (5) Definitely related.

8.3.3.3 EXPECTEDNESS

Site PIs will be responsible for determining whether an adverse event (AE) is expected or unexpected in this NIMBLE clinical trial. An AE will be considered unexpected if the nature, severity, or frequency of the event is not consistent with known ultrasound risks and complications, which are very limited.

8.3.4 TIME PERIOD AND FREQUENCY FOR EVENT ASSESSMENT AND FOLLOW-UP

The occurrence of an AE or SAE may come to the attention of study personnel during ultrasound scans or screening visits. Any medical condition that is present at the time that the participant is screened will be considered as baseline and not reported as an AE. However, if the study participant's condition deteriorates at any time during the study, it will be recorded as an AE.

8.3.5 ADVERSE EVENT REPORTING

The site investigators will record adverse events and report them to the NIMBLE leadership, and to MGH and UCSD IRBs according to the timetable for reporting specified in the protocol. Any AE regarding research participants' health will be reported in 10 working days after the AE becomes known.

Abnormal liver function tests and elevated blood lipids can be accepted as Disease-Related Events (DRE). These DREs are common in the target study population, patients with NAFLD. High liver function test and blood lipids are not associated with ultrasound exam. These factors will not be reported as adverse events.

8.3.6 SERIOUS ADVERSE EVENT REPORTING

In case of a serious adverse event, the site investigator will inform NIMBLE leadership and the MGH or UCSD IRBs as soon as possible, but in no event later than 10 working days after the site investigator first learns of the effect. NIMBLE leadership is responsible for conducting an evaluation of an unanticipated adverse device effect and shall report the results of such evaluation to the FNIH and MGH or UCSD IRB and participating investigators within 10 working days after NIMBLE first receives notice of the effect. Thereafter, the sponsor or designee (i.e. NIMBLE Leadership) shall submit such additional reports concerning the effect as FDA requests.

8.3.7 REPORTING EVENTS TO PARTICIPANTS

Any AE regarding research participants' health will be reported to participant's physician, or in the absence of a physician directly to the participant, via phone call or secure e-mail in 72 hours or less after the PI becomes aware of the AE. AE management strategies and next steps will be handled by the participant's physician.

8.3.8 EVENTS OF SPECIAL INTEREST

This section is not applicable to this protocol.

8.3.9 REPORTING OF PREGNANCY

Women who state they know they are pregnant will be excluded from the study. Pregnancy might increase the intra-abdominal pressure which in turn might affect the reproducibility of elastographic measurements.

8.4 UNANTICIPATED PROBLEMS

8.4.1 DEFINITION OF UNANTICIPATED PROBLEMS (UP)

In this clinical study, UP will be accepted as any incident, experience, or outcome that meets all of the following criteria:

- Unexpected in terms of nature, severity, or frequency given (a) ultrasound scans that are described in this protocol and NIMBLE 1.1 Ultrasound Imaging Manual; and (b) the characteristics of the NAFLD population being studied;
- Related or possibly related to participation in the research (“possibly related” means there is a reasonable possibility that the incident, experience, or outcome may have been caused by the ultrasound scan); and
- Suggests that the research places participants or others at a greater risk of harm (including physical, psychological, economic, or social harm) than was previously known or recognized.

In this clinical study, unanticipated adverse device effects will be accepted as, any serious adverse effect on health or safety or any life-threatening problem or death caused by, or associated with, ultrasound systems, if that effect, problem, or death was not previously identified in nature, severity, or degree of incidence in this protocol or any other unanticipated serious problem associated with ultrasound that relates to the rights, safety, or welfare of participants.

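### The unanticipated-problem definition ties possible relatedness to the ultrasound scan alone, so an event only possibly due to the blood draw misses the 24- or 72-hour report (minor)

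*Combined protocol and SAP*

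**What the plan says.** **UP definition (Section 8.4.1).** A UP is an event that "meets all of the following criteria". In outline, the three criteria are that the event is unexpected, that it is related or possibly related, and that it points to more risk than was known before. The second criterion opens broadly, with "Related or possibly related to participation in the research". A parenthesis then says that possibly related means "there is a reasonable possibility that the incident, experience, or outcome may have been caused by the ultrasound scan". The first criterion is also anchored to the ultrasound scans, together with the characteristics of the NAFLD population.

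**Scope of the study procedures.** Section 6.1.1 states: "Study interventions will include questionnaires, anthropometric measurements, blood collection, and non-invasive ultrasound-based imaging exams". Section 8.3.1 lists among the anticipated non-serious events "Potential discomfort related to IV stick following blood draw at screening".

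**Causality scale (Section 8.3.3.2).** "All AEs will have their relationship to study procedures assessed by the site principal investigator". The scale runs from 0 to 5 and contains "2) Potentially related, (3) Potentially related".

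**Expectedness (Section 8.3.3.3).** An adverse event is unexpected if its nature, severity or frequency "is not consistent with known ultrasound risks and complications".

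**Reporting times to the IRBs and NIMBLE leadership.** A UP that is an SAE is due in 24 hours and any other UP in 72 hours (Section 8.4.2). Outside the UP route, an AE is due in 10 working days (Section 8.3.5). An SAE is due as promptly as possible, with 10 working days as the outer limit (Section 8.3.6).

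**The concern.** The second UP criterion narrows its own scope. It begins with participation in the research as a whole and ends with one procedure. The blood draw is a study intervention and a recognised source of adverse events, and it is the only procedure that breaks the skin. Yet an event that might be due to it cannot be possibly related under the definition given.

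What is at stake is the speed of the report to the IRBs and NIMBLE leadership. That speed matters somewhat more here because the study has no safety oversight committee (Section 10.1.6) and no external clinical monitoring (Section 10.1.7). The UP report is therefore the fast route to independent review.

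The causality scale has its own fault. Two codes share one label, and no code uses the term on which the UP test turns. A site investigator who has graded an event 2 or 3 is not told whether that grade meets the UP relatedness criterion.

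**Working it through.** This is a check of wording; no sample size, power or error rate is involved. I followed one hypothetical event through the rules: an unexpected event that suggests a newly recognised risk, for which the blood draw is a possible but not established cause and the scan is not a plausible cause.

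1. **Criterion 1 (unexpected).** Taken as met. The criterion refers to the ultrasound scans and the NAFLD population and does not mention the blood draw.
2. **Criterion 3 (greater risk than known).** Taken as met. This is a real restriction: ordinary discomfort from the blood draw is already a named risk (Sections 2.3.1 and 8.3.1) and would normally fail here.
3. **Criterion 2, 'related'.** Not met, because the event is only possibly due to a study procedure.
4. **Criterion 2, 'possibly related'.** Not met as defined, because the parenthesis requires that the scan may have been the cause.
5. **Result.** Criterion 2 fails. All three are required, so the event is not a UP and the Section 8.4.2 times do not start.

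Under Section 8.3.3.2 the same event would be graded as potentially related to a study procedure. The two sections therefore classify it differently.

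Times for notice to the IRBs and NIMBLE leadership:

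| Event only possibly due to the blood draw | If it were a UP (8.4.2) | As written |
|---|---|---|
| Serious | 24 hours | As promptly as possible, limit 10 working days (8.3.6) |
| Not serious | 72 hours | 10 working days (8.3.5) |

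At five working days a week, 10 working days is 10 / 5 = 2 weeks, or 14 calendar days without holidays. The limit therefore moves from 1 day or 3 days to about 14 days.

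**How many events.** About 50 people are to be screened (Section 5.5). The investigator may skip the draw when laboratory results from the last three months exist (Section 1.3, footnote c). Screening may fall on the same day as Visit 1 (footnote a); an event after both procedures could be possibly due to the scan as well, and would then qualify. The affected set is very small.

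**Causality scale.** There are six codes (0, 1, 2, 3, 4, 5) and five distinct labels: not, unlikely, potentially (twice), probably and definitely related. None reads 'possibly related', and neither Section 8.3.3.2 nor Section 8.4.1 maps codes to the UP criterion.

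**Expectedness.** Section 8.3.3.3 uses ultrasound risks only. Read literally, blood-draw discomfort, which Section 8.3.1 lists as anticipated, would be unexpected. This mismatch makes more events unexpected, not fewer, so it plays no part in the delay.

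**The case against.** The strongest reply is that this is a drafting slip in a minimal-risk study. The blood volume is about 10 mL or less and is taken by trained phlebotomists (Section 8.1), and no SAEs are anticipated (Section 8.3.2). A sensible investigator would read the parenthesis in the light of the broad opening words. For an event to be affected it must be only possibly due to the draw, unexpected, and a sign of greater risk than was known.

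Existing safeguards also remain. Sections 8.3.5 and 8.3.6 still bring the event to the IRBs and NIMBLE leadership, and for an SAE 10 working days is a limit, not a target. Section 8.3.7 still requires notice of a health-related AE to the participant's physician, or to the participant if there is none, within 72 hours, whatever the cause.

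All of this stands and sets the size of the point. It does not make the definition correct: a rule that starts a 24-hour clock should not depend on the reader disregarding its own parenthesis.

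A reader might also infer four stronger claims that the documents do not support:

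- **The duplicated code lets events escape.** It does not. The Section 8.3.3.2 scale covers all study procedures, blood draw included. The delay comes from the parenthesis alone.
- **The expectedness rule lets events escape.** Section 8.3.3.3 errs in the other direction, and Section 8.4.1 has its own unexpectedness criterion.
- **An inadvertent disclosure of health information would escape.** Disclosure of data held for the study would ordinarily be related to participation, not merely possibly related, and the third criterion expressly extends to psychological, economic and social harm.
- **The shared label spoils a comparison between sites.** Section 9.4.4 plans no analysis of adverse events beyond recording them, so no planned result depends on it.

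**Conclusion.** The text is wrong as written, and the consequence is minor. Section 8.4.1 excludes from the UP definition an event that is only possibly due to the blood draw, although the same criterion opens with participation in the research and Sections 6.1.1 and 8.3.3.2 treat the draw as a study procedure. For such an event the limit for notice to the IRBs and NIMBLE leadership moves from 24 or 72 hours to 10 working days.

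This rests on three assumptions: the parenthesis is applied literally, an event of merely possible causality is not counted as related, and the other two criteria are met. Events judged related to participation through the draw still qualify. It would be wrong to conclude that events go unreported; what is lost is the expedited UP report.

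The duplicated label in Section 8.3.3.2 is a separate and certain error. It makes codes 2 and 3 indistinguishable and leaves the link to the UP test undefined. Neither defect affects the sample size or the primary analysis.

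**What to change.** - **Section 8.4.1, second criterion.** Replace the reference to the scan in the parenthesis with wording that covers all study procedures or participation in the research.
- **Section 8.4.1, first criterion.** Widen the reference to ultrasound scans in the same way, so that both criteria have the same scope.
- **Section 8.3.3.2.** Give codes 2 and 3 distinct labels and state which codes count as possibly related for the UP test. Carry the change into the CRF code list.
- **Section 8.3.3.3.** Reconcile the expectedness reference with the anticipated events in Section 8.3.1. This is a consistency edit only.

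The cost is a few wording changes and one code list, submitted for IRB approval like any other amendment. If events have already been coded 2 or 3, they would need to be regraded or reported as one category. The downside is possibly a few more expedited reports.
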